5.2. Strengths and limitations

5.2.1. Strengths

First, the high retention rate and stability of KPSC membership provide a unique opportunity to follow patients over time and conduct long-term effectiveness studies. More than 90% of members remain in the KPSC health plan after one year; more than three-quarters remain after 3 years. The large, diverse, and stable population makes rapid accrual of a large, representative sample size possible to evaluate long-term implications of vaccination.

Second, Kaiser Permanente Health Connect, KPSC's comprehensive EHR system, is one of the largest private EHR systems in the world. Kaiser Permanente Health Connect and KPSC's integrated model securely connect medical offices and hospitals across the region, providing members, physicians, and other authorized health care providers with online access to clinical information. The system integrates all aspects of care, including pharmacy and lab services, as well as appointments, registration, and billing. This robust system facilitates research by providing comprehensive EHR data for the research team. Care received in the outpatient, inpatient, and emergency settings is documented in the EHR and captured in research databases. Care received outside the KPSC system is captured through claims. Up-to-date details of patient care are available and accessible to researchers near real-time.

Third, chart reviews will be performed to identify and confirm PHN cases, rather than identifying them by diagnosis codes only. Given the expected low positive predictive value and negative predictive value of diagnosis codes for PHN, all HZ cases with encounters during ≥ 3 to 6-month period after HZ diagnosis will be chart reviewed for the occurrence of PHN.

Fourth, for the safety objectives, SCCS analysis will be conducted among individuals with RA or IBD who receive at least one dose of RZV. The SCCS design is a case-only method, in which each case serves as their own control. A major advantage of this design is that the potential confounding by characteristics that vary between individuals and may have an impact on disease outcomes, such as comorbidities and genetic and socioeconomic factors are removed [Farrington, 1995; Wilson, 2011]. Additionally, with comparison periods within close proximity to the risk period (before and after the risk period), the design also controls for time-varying covariates such as age and seasonality. Furthermore, chart review will be performed to ascertain RA and IBD flares.

5.2.2. Limitations

First, confounding by indication is a potential limitation. For the VE objectives, this will be addressed by matching on condition (RA, UC, CD), age, sex, race/ethnicity (if sample size allows), and medication category, which may impact the development of the outcome and likelihood of RZV vaccination. For the safety objectives, the SCCS design mitigates bias through implicit control for time-fixed confounders. While the short risk window minimizes changes in confounders during follow-up, potential confounders will be assessed and adjusted for in final analysis.

Second, a potential limitation is misclassification of exposures and outcomes. However, receipt of RZV should be accurately captured in the EHR system, including dates of administration such that receipt of dose 1 and dose 2 are correctly ascertained. The effectiveness outcome of incident HZ is expected to be accurately captured using an algorithm based on a combination of an International Classification of Diseases (ICD)-10 code and prescription for an antiviral. This algorithm has been used in previous studies and was found to have high accuracy in identifying incident HZ [Capistran, 2021; Langan, 2013; Tseng, 2020; Zhang, 2012]. Given the complexity and significant potential for misclassification of the safety outcome of disease flare, medical record review using standardized criteria will be performed to ascertain this outcome. Since this study uses EHR data, the effectiveness and safety outcomes being captured are those for which medical attention is sought. Mild outcomes may be missed.

Third, there is a potential concern for missing patient data during the course of follow-up, particularly for the longer follow-up duration required for the primary effectiveness outcome. However, patients within KPSC are incentivized to use care inside the health care system, so it is expected that the majority of care, including rheumatologist and gastroenterologist visits, will occur within network, and that there will be comprehensive longitudinal capture of a patient's baseline disease activity, medication regimens, and flares so long as they remain KPSC members.

Fourth, a potential limitation is generalizability. However, the patient population within KPSC exhibits significant racial/ethnic diversity, and the age distribution of patients with RA or IBD in this health care network are expected to reflect the distribution nationally. In addition, although the practices of care for patients with RA and IBD (e.g., treatment regimens) are expected to be largely standardized across U.S. health care systems, the results of this study may not be generalizable to patients who receive care in very different health systems in the U.S.

Finally, the coronavirus disease 2019 (COVID-19) pandemic has significantly affected vaccine uptake in general and in the study patient populations specifically. The pandemic has also indirectly impacted behaviors and policies such as health care delivery, insurance eligibility, and health care-seeking behaviors, and ascertainment of and control for these known and unknown variables may not be fully possible. Thus, subjects will not be accrued in the study from March through December 2020. KPSC will continue to monitor RZV uptake in these patient populations in the KPSC system on a regular basis during study conduct.

6. VARIABLES

The RA and IBD cohorts are detailed in Section 7.2.

6.1. Exposures (VE and Safety)

RZV vaccine doses will be identified using CVX code 187: Zoster vaccine recombinant.

6.1.1. VE

Although RZV should be administered as 2 doses separated by 2-6 months, ACIP guidance followed at KPSC specifies that a second dose administered <4 weeks after the first dose should be repeated, but a second dose administered ≥ 4 weeks after the first dose does not need to be repeated [Anderson, 2022]. Furthermore, due to variation in real-world practice, the second dose may be given earlier than 2 months after the first dose or later than 6 months after the first dose. Additionally, as of January 21, 2022, ACIP guidelines indicate that the second dose of RZV can be administered 1–2 months after the first dose for individuals who are or will be immunodeficient or immunosuppressed and who would benefit from a shorter vaccination schedule [Anderson, 2022]. Therefore, VE objectives refer to 2 doses of RZV given at least 4 weeks apart through the end of the study accrual, except where indicated otherwise.

The exposure for primary VE objectives 1-2 is 2 doses of RZV with the second dose received 4 weeks to 6 months after the first dose through the end of study accrual. The exposure for secondary VE objectives 1-3 and 5 and exploratory VE objectives 1-4 is 2 doses of RZV, with the second dose received at least 4 weeks after the first dose (“2-dose [≥ 4 weeks]”). The exposure for secondary VE objective 4 is 2 doses of RZV, with the second dose received >6 months after the first dose through the end of study accrual. The index date will be date of receipt of the second RZV dose.

[figure not shown]
The exposure for secondary VE objectives 6-7 is 1 dose of RZV. The index date will be date of receipt of the first RZV dose. The 1-dose VE will be evaluated in individuals who receive 1 dose of RZV and do not receive a second dose within 6 months after the first dose.

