Individuals will be followed through the KPSC EHR from 31 days after the index date until occurrence of HZ, termination of membership (allowing for a 31-day gap in membership), death, receipt of a dose of zoster vaccine (receipt of a third dose of RZV for 2-dose vaccinated individuals, receipt of a second dose of RZV for 1-dose vaccinated individuals, receipt of a first dose of RZV for unvaccinated individuals, or receipt of ZVL), or end of the study period, whichever comes first. Individuals are followed from 31 days after index date to allow sufficient time for development of immunity in the vaccinated cohort and to avoid capture of pre-existing HZ episodes. Cox proportional hazards regression will be used to assess the HR for HZ comparing RZV vaccinated and unvaccinated individuals with RA or with IBD (UC and CD). VE will be calculated from the HR. Secondary analyses will stratify VE by UC and CD, by age group (18-49 years and ≥ 50 years [≥ 50 years, 50-59 years, 60-69 years, and ≥ 70 years]), and by timing of the second dose of RZV (second dose given >6 months after first dose, second dose given at least 4 weeks after first dose). Additional secondary analyses will examine VE after one dose of RZV with the index date as the date of receipt of the first RZV dose. Additional exploratory analyses will also be conducted.

For the safety objectives, an SCCS analysis will be conducted among individuals aged ≥ 18 years with RA or IBD who receive at least one dose of RZV. The date of vaccination with the first dose of RZV will be defined as Day 0. Given the complexity of accurately ascertaining disease flares, the EHR will be reviewed for these individuals for occurrence of flares rather than relying on administrative data. A flare will be identified by documented contact with a health care provider, and new or worsening signs and/or symptoms suggestive of a flare, and a change in medication for flare ([Appendix 2](#)). For primary analyses, the RR of flare in pre-defined risk periods compared to comparison periods will be assessed for RA and IBD (details in Section 6.1.2). Secondary analyses will stratify the risk of flares by UC and CD. Exploratory analyses will stratify the risk of flares by medication category at baseline.

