7.4. Matching for VE analyses

For secondary VE objectives 1-3, secondary VE objective 5, and exploratory VE objectives 1-4, individuals meeting inclusion criteria who receive 2 doses of RZV at least 4 weeks apart through the end of the accrual period will be matched with unvaccinated individuals who have not received any doses of RZV as of the index date at a ratio of 1 to up to 3. For secondary VE objective 4, individuals meeting inclusion criteria who receive 2 doses of RZV >6 months apart through the end of the accrual period, and for primary VE objectives 1-2, individuals meeting inclusion criteria who receive 2 doses of RZV 4 weeks to 6 months apart, and their respective matched unvaccinated comparators will be included. No separate matching is needed.

Matching variables will comprise the following:

- Condition (RA, UC, CD)
- Age (by decade) at index date
- Sex
- Race/ethnicity, if sample size allows
- Medication category at index date (detailed in [Appendix 3](#)).

For secondary VE objectives 6-7, individuals who receive 1 dose of RZV but do not receive a second dose 4 weeks to 6 months after the first dose will be matched with unvaccinated individuals who have not received any doses of RZV as of the index date at a ratio of 1 to up to 3. The 1-dose person-time will be censored upon receipt of the second RZV dose received >6 months after the first dose. Matching variables will comprise condition (RA, UC, CD), age (by decade) at index date, sex, race/ethnicity (if sample size allows), and medication category at index date.

The 2-dose (4 weeks to 6 months) RZV cohort and 1-dose RZV cohort will be mutually exclusive. Unvaccinated individuals who are matched to RZV vaccinated individuals can contribute person-time to a vaccinated cohort if they receive RZV; their unvaccinated person-time is censored upon receipt of the first dose of RZV.

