11.2.3. Secondary analyses

For secondary and exploratory analyses, subgroups may be recategorized in post-hoc analyses if sample size in a subgroup is small

Secondary VE objectives 1-3: Analyses for secondary VE objectives 1-3 (2 doses of RZV given at least 4 weeks apart) will employ similar methods as for the primary VE analyses. In secondary VE objective 1, analyses for IBD (primary VE objective 2) will be stratified by UC and CD. In secondary VE objective 2, analyses for RA (primary VE objective 1) will be stratified by age group (18-49 years and ≥ 50 years [≥ 50 years, 50-59 years, 60-69 years, and ≥ 70 years]). In secondary VE objective 3, analyses for IBD (primary VE objective 2) will be stratified by age group (18-49 years and ≥ 50 years [≥ 50 years, 50-59 years, 60-69 years, and ≥ 70 years]). Descriptive analyses and multivariable Cox proportional hazards regression will be conducted by strata and estimates of VE (%) will be calculated as $(1 - \text{adjusted HR}) \times 100$.

Secondary VE objectives 4-5: Analyses for secondary VE objectives 4-5 will employ similar methods as for the primary VE analyses. For secondary VE objective 4, the 2-dose RZV cohort will include individuals who receive their second dose >6 months after the first dose during the accrual period. For secondary VE objective 5, the 2-dose RZV cohort will include individuals who receive their second dose at least 4 weeks after the first dose during the accrual period. Analyses will be stratified by condition (RA or IBD). The VE of 2 doses (≥ 4 weeks apart) of RZV by time since vaccination will also be evaluated.

Secondary VE objectives 6-7: Analyses for secondary VE objectives 6-7 will be conducted among the matched cohorts of individuals with RA (secondary VE objective 6) or with IBD (secondary VE objective 7) who receive 1 dose of RZV and do not receive a second dose within 6 months after the first dose. Individuals will be followed from 31 days after the index date until occurrence of HZ, termination of membership, receipt of a dose of RZV for unvaccinated individuals, receipt of a second dose of RZV >6 months after the first dose among vaccinated individuals, or end of study period, whichever comes first. Descriptive analyses and multivariable Cox proportional hazards

regression will be conducted and estimates of VE (%) will be calculated as $(1 - \text{adjusted HR}) \times 100$. The VE of 1 dose of RZV by time since vaccination will also be evaluated.

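### Entry to the 1-dose VE cohort depends on dose-2 status over the 6 months after dose 1, but follow-up starts on day 31, so VE between day 31 and month 6 can be biased in either direction

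*Protocol*

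**What the plan says.** Three places in the protocol fix the 1-dose cohort for secondary VE objectives 6-7.

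- Section 6.1.1 evaluates 1-dose VE in "individuals who receive 1 dose of RZV and do not receive a second dose within 6 months after the first dose" and sets the time origin: "The index date will be date of receipt of the first RZV dose".
- Section 7.4 matches "individuals who receive 1 dose of RZV but do not receive a second dose 4 weeks to 6 months after the first dose". A later second dose is handled differently: "The 1-dose person-time will be censored upon receipt of the second RZV dose received >6 months after the first dose". The section also makes the 1-dose cohort and the 2-dose (4 weeks to 6 months) cohort mutually exclusive.
- Section 11.2.3 repeats the 6-month condition and starts the clock: "Individuals will be followed from 31 days after the index date until occurrence of HZ".

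The comparators in section 7.4 are "unvaccinated individuals who have not received any doses of RZV as of the index date". If they are vaccinated later, "their unvaccinated person-time is censored upon receipt of the first dose of RZV", so their earlier time is kept.

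Section 5.1 lists "receipt of a second dose of RZV for 1-dose vaccinated individuals" among the general censoring events. Section 11.2.3 plans 1-dose VE by time since vaccination.

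**The concern.** Cohort entry is settled up to five months after at-risk time begins, and in the vaccinated arm only. A first-dose recipient who receives dose 2 between 4 weeks and 6 months is removed together with all earlier 1-dose time and any HZ event in it. One whose dose 2 slips past 6 months is kept, with any event. If HZ, or something that goes with it such as illness, alters whether dose 2 is given on time, then the events counted between day 31 and month 6 do not represent the 1-dose experience in that interval.

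The estimates at stake are 1-dose VE in RA and in IBD, above all any early band in the analysis by time since vaccination. A band reported on its own could be misread as poor, or unusually good, early protection from a single dose.

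**Working it through.** **Reading the rules together.** The protocol gives no sample size, power or VE figure for the 1-dose objectives, so there is no stated result to reproduce. Setting the rules side by side shows three things.

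1. At day 31 the plan uses a proper landmark in both arms. Section 7.2.1 requires membership to 31 days after index. Section 7.2.2 excludes HZ, zoster vaccination or death within 30 days, and follow-up starts after that. The 6-month condition has no matching start of follow-up and binds one arm.
2. The censoring rule in section 5.1 cannot repair this, because people with dose 2 in the first 6 months never enter the cohort.
3. A person with HZ after day 31 who still gets dose 2 within 6 months is outside the 1-dose cohort. That HZ also falls in the 6 months before dose 2, so section 7.2.2 excludes the person from the 2-dose cohort. The event is counted in no vaccinated cohort.

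**Inputs.**

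- Completion share p: Table 5 gives 1843/3071 = 0.60 for RA and 1385/2308 = 0.60 for IBD. Its yearly rows do sum to 1843 and 1385, and section 11.1.1 describes these as recipients of two doses 4 weeks to 6 months apart.
- HZ rate in the unvaccinated: 15 per 1000 person-years (section 11.1.1). Average follow-up: 3.5 years.
- Assumptions not in the protocol: a true 1-dose VE of 70% (60% in the simulation), dose 2 spread evenly over days 60-183, and q, the share of people with HZ before a planned dose 2 who then miss the 6-month window.

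**Size in days 31-183 if HZ delays dose 2.** Per first-dose recipient, the 1-dose cohort would have events in proportion to (1 − p) × 152 days. Completers have events before dose 2 in proportion to p × m, where m is the mean time from day 31 to dose 2. A share q of those events is added to the cohort. So

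inflation of the early rate = 1 + p·m·q / ((1 − p)·152)

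With m = (60 + 183)/2 − 31 = 90.5, this is 1 + (0.60 × 90.5 × q)/(0.40 × 152) = 1 + 0.893q.

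To relate q to behaviour, suppose HZ moves dose 2 to at least d days after the HZ. Then q = (d²/2)/(123 × 90.5) for d up to 90. This gives 450/11131.5 = 4%, 1800/11131.5 = 16% and 4050/11131.5 = 36% for d = 30, 60 and 90.

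| q | inflation | VE days 31-183 (true 70%) |
|---|---|---|
| 0 | 1.00 | 70% |
| 0.04 | 1.04 | 69% |
| 0.16 | 1.14 | 66% |
| 0.36 | 1.32 | 60% |
| 0.50 | 1.45 | 57% |

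**If HZ prompts dose 2.** When a share r of would-be non-completers with HZ receive dose 2 inside the window, their events leave the cohort and the early rate is multiplied by about 1 − r. With true VE 60%, r = 0.25 gives 1 − 0.40 × 0.75 = 70%, and r = 0.50 gives 80%.

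**Whole follow-up.** Days 31-183 are 152 of 3.5 × 365.25 − 31 = 1247 days, or 12.2%. Overall inflation is therefore about 1 + 0.122 × 0.893q = 1 + 0.109q. With true VE 70%, q = 0.50 gives 1 − 0.30 × 1.054 = 68.4%.

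**Simulation check.** Eight million first-dose recipients were simulated with true VE 60% and dose 2 even over days 28-183.

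| scenario | VE days 31-183 | VE over 3.5 years | VE after month 6 |
|---|---|---|---|
| q = 0 | 60% | 60% | 60% |
| q = 0.25 | 52% | 59% | 60% |
| q = 0.50 | 45% | 58% | 60% |
| q = 1 | 31% | 56% | 60% |
| r = 0.25 | 70% | 61% | 60% |
| r = 0.50 | 80% | 62-63% | 60% |

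In the same runs, censoring at dose 2 whenever given returned 59-60% for days 31-183, and a 6-month landmark returned 60%, in every scenario.

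**The case against.** A reader might infer that 1-dose VE is biased as a matter of course, and downward, because cases are kept while event-free time is thrown away. The documents do not support that.

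- People with HZ who still receive a timely dose 2 are removed along with their event. When dose-2 timing is independent of HZ, events and time are dropped in proportion and the true VE is recovered.
- Nothing in the protocol says how HZ affects dose-2 uptake, so the sign is open.
- Large distortions need outright cancellation or long postponement. Under the assumed schedule, a 30-day deferral gives q of about 4%.
- The numbers are small. About 3071 − 1843 = 1228 RA and 2308 − 1385 = 923 IBD recipients remain. At 15 per 1000 person-years and VE 70%, days 31-183 yield 1228 × (152/365.25) × 0.0045 = 2.3 RA events and 1.7 IBD events. At q = 0.50 the bias adds about one event per condition. Section 11.1.1 already warns that secondary analyses may be underpowered.
- The protocol gives no time bands, so it is unknown whether an early band will be reported alone.
- The plan may deliberately target people who do not complete within 6 months.

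All of this stands, and it limits the direction, size and urgency of the point. It does not remove the structural fault. The target population explains the restriction but not a start of follow-up at day 31. Section 5.2.2 does not list the issue as a limitation, and item 10.8 of the EnCePP checklist says no sensitivity analyses are planned.

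**Conclusion.** The concern holds as a conditional one. For secondary VE objectives 6-7, the selection rule makes VE between day 31 and month 6 depend on how HZ changes later dose-2 uptake: downward if HZ delays or cancels it, upward if HZ prompts it, unbiased if neither. Under the assumed schedule and a true VE of 70%, the early estimate reads about 69% to 57% for q from 4% to 50%. Over 3.5 years the loss is about 1 to 4 points for q from 25% to 100% (true VE 60%), and smaller for smaller q.

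This mechanism leaves VE after month 6 unaffected. The primary objectives are also unaffected, because their index date is dose 2. The 60% completion comes from Table 5; q, r, the dose-2 schedule and the true 1-dose VE are assumptions. The rule should be changed, but it does not threaten the main conclusions of the study.

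**What to change.** Amend sections 6.1.1, 7.4 and 11.2.3 in one of two ways.

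- **Censoring.** Enter every eligible first-dose recipient, count 1-dose person-time from day 31, and censor at dose 2 whenever it is given. Replace mutually exclusive cohorts with mutually exclusive person-time. Cost: much of the 1-dose time is short, and the target population widens to all first-dose recipients.
- **Landmark.** Keep the population who do not complete within 6 months, but start follow-up 6 months after dose 1. On that date, require 1-dose recipients and comparators alike to be enrolled, HZ-free since index and without a further zoster vaccine dose (none at all of RZV for comparators). Cost: VE in the first 6 months is not estimated.

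Either option needs revised wording and a re-run of the 1-dose match, with no new data. The choice depends on whether the question is protection while awaiting dose 2 or protection in those who do not complete on time; the amended text should say which.

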6.1.2. Safety

An SCCS design (Figure 1) will be used. For patients receiving only 1 dose of RZV, the date of vaccination with the first dose of RZV will be defined as Day 0, the risk period will be defined as +1 to +30 days, and comparison periods will be defined as -90 to -61 days and +31 to +60 days (Figure 1, Individuals received only one dose). The washout period will be defined as -60 to -1 days. The 30-day risk period was determined based on prior literature, vaccine mode of action, and consultation with external physician experts (rheumatologists and gastroenterologists) [Basra, 2012; Didierlaurent, 2017].

For individuals who receive a second dose of RZV within 300 days of the first RZV dose, there are several scenarios for additional risk and comparison periods. If the second dose is received between +28 to +90 days after the first dose, the risk period after the first dose will be immediately followed by a washout period up to receipt of the second dose (Figure 1, Scenario 1). If the second dose is received between +91 to +150 days after the first dose, the risk and comparison periods following the first dose will be followed by a 60-day washout period immediately before the receipt of the second dose (Figure 1, Scenario 2). If the second dose is received between +151 days to +300 days after the first dose (expected to be less common), there will be a comparison period -90 to -61 days prior to the second dose and a washout period -60 to -1 days prior to the second dose (Figure 1, Scenario 3). In Scenario 1, the risk window after the first dose could be between 28 and 30 days and the subsequent washout window could be between 0 and 60 days. In Scenario 2, the comparison window between 2 doses could be between 1 and 60 days. The maximum follow-up period will be 360 days after the first dose. Scenarios 2-4 in Figure 1 represent the maximum time period between the first and second dose

Figure 1 SCCS Design Overview for Safety Analysis

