6.2.2. Safety

The outcome for primary safety objectives 1-2, secondary safety objective 1, and exploratory safety objectives 1-2 is flare, defined as new-onset flare or new-onset of disease worsening of RA (primary safety objective 1, exploratory safety objective 1) or IBD (UC or CD) (primary safety objective 2, secondary safety objective 1, exploratory safety objective 2). Flare will be identified through EHR review by trained research associates and RA or IBD specialists. Events are counted in the period in which earliest symptom onset occurs. Clinically relevant flare is described in [Appendix 2](#).

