Chart review will be performed among individuals eligible for the safety analysis. Trained research associates will review medical records from health care encounters during risk windows, comparison windows, and the 30 days after a risk or comparison window (while masked to the precise window) for evidence of flare. They will identify new or worsening signs and/or symptoms suggestive of a flare and capture the date of onset of new or worsening signs and/or symptoms. They will determine whether a change in medication was made for flare by a provider. Cases with unclear sign and/or symptoms, date of onset, or change in medication for flare will be reviewed by an RA or IBD specialist.

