10.6: Outcome misclassification will be accounted for in non-analytic ways; it will be controlled by chart confirmation of PHN and flare outcomes as well as an algorithm for HZ detailed in Section 6.2.1.

10.7: Methods for handling missing data will be addressed in the SAP.

10.8: No sensitivity analyses are planned for this study.

Section 11: Data management and quality control	Yes	No	N/A	Section Number
11.1 Does the protocol provide information on data storage? (e.g. software and IT environment, database maintenance and anti-fraud protection, archiving)				13.5.2
11.2 Are methods of quality assurance described?				13.5.3
11.3 Is there a system in place for independent review of study results?				

Comments:

11.3: There is no independent data monitoring committee for this observational study.

Section 12: Limitations	Yes	No	N/A	Section Number
12.1 Does the protocol discuss the impact on the study results of:				
12.1.1 Selection bias?				5.2.2
12.1.2 Information bias?				5.2.2
12.1.3 Residual/unmeasured confounding? (e.g. anticipated direction and magnitude of such biases, validation sub-study, use of validation and external data, analytical methods).				5.2.1 and 5.2.2
12.2 Does the protocol discuss study feasibility? (e.g. study size, anticipated exposure uptake, duration of follow-up in a cohort study, patient recruitment, precision of the estimates)				5.1, 7.1, and 11.1

Comments:

Nil

Section 13: Ethical/data protection issues	Yes	No	N/A	Section Number
13.1 Have requirements of Ethics Committee/ Institutional Review Board been described?				13.5.1 and 13.5.2

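### Flares with onset on the day of the first RZV dose fall in no SCCS window, so the planned safety analysis cannot show clustering on the vaccination day

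*Protocol*

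**What the plan says.** Protocol Section 6.1.2 fixes the time axis: "the date of vaccination with the first dose of RZV will be defined as Day 0". On that axis, for patients with a single dose, "the risk period will be defined as +1 to +30 days, and comparison periods will be defined as -90 to -61 days"; a second comparison period covers +31 to +60. The days just before the dose are set aside: "The washout period will be defined as -60 to -1 days". Section 1.3 and the power calculation in Section 11.1.2 use the same risk and comparison windows.

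Flares are placed by onset, not by contact or treatment date. Section 6.2.2: "Events are counted in the period in which earliest symptom onset occurs". Section 11.2.2 then estimates the relative risk by conditional Poisson regression from risk and comparison periods only, overall and by dose.

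Appendix 2 has reviewers read "health care encounters during risk windows, comparison windows, and the 30 days after a risk or comparison window" and record the onset date. The EnCePP checklist (Section 13.5.8, comment 10.8) adds: "No sensitivity analyses are planned for this study".

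For a second dose, Section 6.1.2 describes three scenarios by dosing interval. Scenario 1 (dose 2 at +28 to +90) is given a dose-1 risk window of 28 to 30 days and a washout of 0 to 60 days. Scenario 2 (+91 to +150) is given a between-dose comparison window of 1 to 60 days. Scenario 3 (+151 to +300) has a washout of -60 to -1 days before dose 2.

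**The concern.** The primary safety objectives (Section 4, Table 1) ask about flares in the 30 days after any RZV dose, and Section 3 gives the motive as a theoretical concern about flare after an adjuvanted vaccine. A flare that starts a few hours after the injection belongs to that question. Suppose such a patient contacts the clinic on day +3 and has a medication change. The chart is read and the onset is dated to Day 0, but no period exists in which to count the event.

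The protocol gives a rationale for the 30-day length of the risk period but none for starting it on day +1, and it plans no analysis that brings Day 0 back. If flares did cluster on the vaccination day, neither the primary relative risk nor any other planned output would show it.

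**Working it through.** **1. Coverage of days, first dose.** From -90 to +60 there are 151 days: comparison 30 (-90 to -61), washout 60 (-60 to -1), risk 30 (+1 to +30), comparison 30 (+31 to +60). These sum to 150. The uncovered day is Day 0.

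**2. Coverage of the dose-2 day.** Let dose 2 fall on day t after dose 1.

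| Stated length (Section 6.1.2) | Dose-2 day left out | Dose-2 day put in the preceding window |
|---|---|---|
| Scenario 1, shortest risk window 28 days (t = 28) | 27 | 28 |
| Scenario 1, longest washout 60 days (t = 90) | 59 | 60 |
| Scenario 2, shortest comparison window 1 day (t = 91) | 91 - 60 - 1 - 30 = 0 | 91 - 60 - 30 = 1 |
| Scenario 2, longest comparison window 60 days (t = 150) | 59 | 60 |

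The stated lengths match only the last column. On that reading, a flare on the dose-2 day counts in the dose-1 risk window if t is 28 to 30, and otherwise falls in washout and is not counted. In Scenario 3 the washout stops at -1, so the dose-2 day is left out as Day 0 is for dose 1. The handling of the dose day therefore differs between scenarios.

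**3. The protocol's own figure.** Inputs from Section 11.1.2: two-sided alpha 0.05, power 80%, k = 2, so r = 1/3. The signed root likelihood ratio formula, with d = RR·r + 1 - r, is

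- A = 2[(RR·r/d)·ln RR - ln d]
- B = [(ln RR)²/A]·RR·r(1 - r)/d²
- n = (1.960 + 0.842·√B)²/A

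At RR 1.5, A = 0.03924, B = 1.0260 and n = 201.6, split 86.4 risk and 115.2 comparison; Table 7 gives 87 and 115. The other rows also reproduce (385.9/643.2, 33.5/33.5, 15.8/10.5). With Day 0 added to the risk window (31 risk and 60 comparison days), n = 200.1, split 87.4 and 112.8. The sample size is essentially unaffected either way.

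**4. Flares lost at background rates, first dose.** N × (30-day rate)/30:

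- RA (Table 8): 3071 × 0.025/30 = 2.6; range 1.5 to 7.2 for rates of 1.5% to 7%.
- IBD (Table 9): 2308 × 0.03/30 = 2.3; range 0.8 to 3.1 for rates of 1% to 4%.

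**5. What the planned relative risk would miss.** The documents give no Day 0 hazard, so this is an assumption: risk on days +1 to +30 equals background (RR = 1), and Day 0 hazard is m times background. The Day 0 to +30 relative risk is then (30 + m)/31.

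| m (assumed) | Planned RR, +1 to +30 | RR, Day 0 to +30 |
|---|---|---|
| 2 | 1.0 | 1.03 |
| 5 | 1.0 | 1.13 |
| 10 | 1.0 | 1.29 |
| 20 | 1.0 | 1.61 |

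**6. Is the event visible in the charts?** For a first dose, the review span is -90 to -61, +1 to +60, and the 30 days after each window. A Day 0 onset with contact from +1 onward is inside that span. A contact on Day 0 itself is not: the first comparison window plus 30 days ends at -31, and the risk window starts at +1.

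**The case against.** The windows are the same wherever they are stated, and starting at +1 is a natural reading of the days following a vaccination. A same-day onset may precede the injection; for zoster, Section 7.2.2 excludes early events partly because of that kind of ambiguity. Figure 1 is not reproduced in the available text and may settle the dose-2 day, and the SAP is not at hand. All of this stands: for dose 1 this is an unexplained design choice, not a contradiction. It does not remove the point, because the protocol itself fixes the windows and the allocation rule, and comment 10.8 rules out sensitivity analyses without deferring them to the SAP.

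A reader might go further and infer that dropping Day 0 lowers only the numerator and biases the primary result toward no harm. The documents do not support that. Day 0 is also outside the risk person-time, so the relative risk is valid for its own window; it differs from a Day 0 to +30 relative risk only if Day 0 hazard differs from that of days +1 to +30.

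A reader might also infer a substantial loss of power. For RA, a true RR of 1.5 on a base of 3071 × 0.025 = 76.8 flares gives 38.4 excess flares. If 10% to 25% of these began on Day 0, the RR would read 1.45 to 1.375 and power would fall from 90% to 84% to 70% (IBD: 87% to 80% to 66%). That share has no source in the documents. It implies 3.8 to 9.6 excess flares on one day against 2.6 expected, a hazard of 2.5 to 4.75 times background. With the excess spread evenly over 31 days the share is 1/31 = 3.2%, and power moves about 2 points (RA 90% to 88%, IBD 87% to 85%). The sum also sets 31 days of excess against a 30-day base; on a 31-day base (76.8 × 31/30 = 79.3) the starting RR is 1 + 38.4/79.3 = 1.48, so part of the apparent attenuation is artefact. Finally, these figures use dose 1 only, whereas the primary relative risk covers both doses.

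**Conclusion.** The point holds in a limited form. A flare with onset on the day of the first dose enters no SCCS window and is counted nowhere. For the second dose this is clear in Scenario 3; in Scenarios 1 and 2 the stated lengths imply that the dose day belongs to the preceding window, which the protocol never says.

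The planned relative risk is not biased for days +1 to +30, and the power calculation stands. What is lost is any view of the vaccination day: about 2 to 3 first-dose flares per cohort at the protocol's central rates, and more only if flares cluster there. The 1.13 and 1.29 figures rest on assumed Day 0 hazards of 5 and 10 times background with no raised risk afterwards; they show what could go unseen, not what is expected. The dose-2 reading rests on the text of Section 6.1.2 without Figure 1. This is a worthwhile, inexpensive improvement rather than a flaw in the primary analysis.

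**What to change.** - **Section 6.1.2:** keep +1 to +30 as the primary risk window. State how the day of each dose is treated and why, and make the Scenario 1 to 3 window lengths agree with that rule.
- **Section 11.2.2:** tabulate flares with onset on a dose day separately, by dose and condition. Pre-specify one supporting analysis with risk window Day 0 to +30 (31 days of risk time), excluding Day 0 flares whose record shows onset before the injection.
- **Section 13.5.8, comment 10.8:** amend so that it no longer says that no such analysis is planned.

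The cost is wording, one table and one further model. Reviewers already record onset dates for contacts from day +1; capturing contacts on Day 0 itself would add one day to the first-dose review span. The downside is that some Day 0 onsets cannot be ordered relative to the injection, so the analysis should stay supportive.
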